4.3.1.2 Sham

Sham vial is empty and will remain empty throughout the sham treatment. It does not contain any lyophilized powder. There is no reconstitution process for the sham vial.

4.3.2 Dosage, Administration, and Compliance

4.3.2.1 Lampalizumab and Sham

Dosage

Study treatment should not occur earlier than 22 days after the previous treatment.

Guidelines for treatment interruption or discontinuation are provided in Section [4.6.2](#) and Section [4.4.3](#).

Any overdose or incorrect administration of study drug should be noted on the Study Drug Administration electronic Case Report Form (eCRF). Adverse events

Lampalizumab—F. Hoffmann-La Roche Ltd
56/Protocol GX29176, Version 6

associated with an overdose or incorrect administration of study drug should be recorded on the Adverse Event eCRF.

Lampalizumab Intravitreal Injections

A 10-mg dose of lampalizumab will be used in this study and will be administered intravitreally to patients randomized to the lampalizumab Q4W or Q6W treatment arms during the 2-year treatment period (see [Appendix 1](#) for the study flowcharts).

Sham Injections

Patients randomized to the control arms will receive sham injections Q4W or Q6W during the 2-year treatment period and will undergo the same assessments as the lampalizumab treatment arm (see [Appendix 1](#) for the study flowcharts).

Sham injection is a procedure that mimics an intravitreal injection of lampalizumab, except that the blunt end of an empty syringe is pressed against an anesthetized eye instead of a needle attached to a lampalizumab-filled syringe.

Administration

See [Appendix 4](#) for the pre-injection procedures of both treatments (lampalizumab and sham) for all patients, [Appendix 5](#) for the injection procedures of the study drug, [Appendix 6](#) for the injection procedures of the sham treatment procedure, and [Appendix 7](#) for the post-injection procedures for all treated patients.

Compliance

This study will be conducted in accordance with the U.S. Food and Drug Administration (FDA) regulations; the International Conference on Harmonisation (ICH) E6 Guideline for Good Clinical Practice (GCP); and applicable local, state, and federal laws, as well as other applicable country laws.

4.3.3 Investigational Medicinal Product Accountability

All investigational medicinal products (IMPs) required for completion of this study (lampalizumab and sham) will be provided by the Sponsor. The study site will acknowledge receipt of IMPs and confirm the shipment condition and content. Any damaged shipments will be replaced.

IMPs will either be disposed of at the study site according to the study site's institutional standard operating procedure or returned to the Sponsor with the appropriate documentation. The site's method of IMP destruction must be agreed to by the Sponsor. The site must obtain written authorization from the Sponsor before any IMP is destroyed. IMP destruction must be documented on the appropriate form.

Accurate records of all IMPs received at, dispensed from, returned to, and disposed of by the study site should be recorded on the Drug Inventory Log.

4.3.4 Post-Study Access to Lampalizumab

The Sponsor will offer post-study access to the study drug lampalizumab free of charge to eligible patients in accordance with the Roche Global Policy on Continued Access to IMPs as outlined below.

A patient will be eligible to receive study drug after the end of the study if all of the following conditions are met:

- The patient has a sight-threatening or severe medical condition and requires study drug treatment for his or her well-being
- There are no appropriate alternative treatments available to the patient
- The patient and his or her doctor comply with and satisfy any legal or regulatory requirements that apply to them

A patient will not be eligible to receive study drug after the end of the study if any of the following conditions are met:

- The study drug is commercially marketed in the patient's country and is reasonably accessible to the patient (e.g., is covered by the patient's insurance or would not otherwise create a financial hardship for the patient)
- The Sponsor has discontinued development of the study drug or data suggest that the study drug is not effective for GA
- The Sponsor has reasonable safety concerns regarding the study drug as treatment for GA
- Provision of study drug is not permitted under the laws and regulations of the patient's country

The Roche Global Policy on Continued Access to IMPs is available at http://www.roche.com/policy_continued_access_to_investigational_medicines.pdf.

4.4 CONCOMITANT THERAPY

4.4.1 Permitted Therapy

Concomitant medications are any prescription drugs or over-the-counter preparations other than protocol-specified procedural medications (e.g., dilating drops or fluorescein dyes) and pre- and post-injection medications (e.g., proparacaine or antimicrobials [if applicable]) used by a patient within 7 days preceding Day 1 visit and through the conclusion of the patient's study participation or early termination visit. All concomitant medications should be reported to the investigator and recorded on the Concomitant Medications eCRF log except of Lucentis[®] for either eye treatment (if applicable), which will have a separate eCRF.

Patients required to use medications that are prohibited (see Section 4.4.2) will not be eligible for the study. Patients who use other maintenance therapies should continue their use. Of note, the following are some common therapies that are permitted:

- Onset of ocular hypertension or glaucoma in the study eye during a patient's study participation should be treated as clinically indicated
- Onset of cataract or posterior capsular opacification in either eye during the patient's study participation may be treated as clinically indicated. Dose-interruption criteria (see Section 4.4.3, Table 4) may apply with cataract surgery.
- Short-term use of topical corticosteroids after cataract surgery, YAG capsulotomy, or peripheral iridotomy
- At the discretion of the evaluating physician, randomized patients who are receiving study treatment may be treated with Lucentis[®] if they are diagnosed in either eye with an ocular condition for which Lucentis is approved in the country. Consult with the region specific Lucentis Prescribing Information for the recommended dose and frequency of treatment.

NOTE: If (as per masked investigator judgment) treatment with Lucentis is to be given (to study and/or non-study eye) at the same visit as a study eye treatment with lampalizumab/sham, the treatment with Lucentis must be administered first. Following this, a safety *assessment* (including an IOP check) *must be completed by the physician in the masked role prior to the study eye treatment with lampalizumab/sham. If there are no concerns, the site may proceed with calling* IxRS for the study treatment kit assignment. Individual trays and sterile prep must be separately prepared for each treatment. The injecting physician will perform the treatment with Lucentis to preserve the masking.

- Oral corticosteroids at doses ≤ 10 mg/day prednisone or equivalent

4.4.2 Prohibited Therapy

At the discretion of the investigator, patients may continue to receive medications and standard treatments administered for other conditions. However, the following medications/treatments are prohibited from use during the patient's participation in the study treatment, and patients will be discontinued from study treatment and/or study to receive these therapies:

- Systemic anti-vascular endothelial growth factor (anti-VEGF) agents
- Intravitreal anti-VEGF agents (other than Lucentis) in either eye
- Intravitreal, subtenon, or chronic topical (ocular) corticosteroids in study eye
- Systemic or intravenous immunomodulatory therapy (e.g., azathioprine, methotrexate, mycophenolate mofetil, cyclosporine, cyclophosphamide, anti-tumor necrosis factors, eculizumab)
- Treatment with Visudyne in study eye
- Other experimental therapies (except those with vitamins and minerals)

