The first study treatment will be administered on the same day as randomization (Day 1 visit). *If a site has an unexpected issue (e.g., the IxRS is not able to assign the study kit), with the Medical Monitor's permission, the patient's first study treatment may be administered within 3 working days of the Day 1 visit. The following assessments will be repeated on the day of the study treatment: slit lamp examination, indirect ophthalmoscopy, and pre- and post-treatment IOP measurement (recorded on Day 1 eCRF and dated accordingly).*

Study treatment visits will be scheduled Q4W (± 5 days) or Q6W (± 5 days) relative to the Day 1 visit date. Randomized patients will have the first intravitreal injection of lampalizumab or sham injection administered by the investigator on Day 1 and will have safety and ocular assessments performed on Day 8 (± 2 days) visit. At the subsequent scheduled visits (Q4W or Q6W), patients will have safety evaluations performed by the investigator prior to receiving study drug or sham injection. They will be contacted by site personnel 4 (± 2) days after each injection to elicit reports of decrease in vision, eye pain, unusual redness, or any other new ocular symptoms in the study eye. If warranted, patients will be asked to return to the clinic as soon as possible for an unscheduled safety assessment visit (see [Appendix 2](#)). Patient self-administered antimicrobials pre- and post-injection may be used at the investigator's discretion. Patients will be instructed to contact the investigator at any time if they have any health-related concerns.

All assessments for a scheduled visit are to be performed on the same day, except those performed during the screening period.

Study treatment should not occur earlier than 22 days after the previous treatment. Missed study treatments will not be made up.

After the Day 1 visit, if a patient misses a study visit when ocular images are scheduled to be taken (see [Appendix 1](#)), the images must be obtained at the next scheduled visit.

Patients are not expected to attend their scheduled visits if there are extenuating circumstances justifying their inability to come to the clinic.

For masking requirements, see [Section 4.2.2](#).

Patients who are prematurely discontinued from study treatment will be encouraged to undergo as many scheduled visits as possible with emphasis on completing Week 48 and Week 96 visits.

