4.6.2 Study Treatment Discontinuation

The investigator has the right to discontinue a patient from the study treatment for any medical condition that the investigator determines may jeopardize the patient's safety if he or she continues in the study treatment, for reasons of non-compliance (e.g., missed doses, visits), if the patient becomes pregnant, or if the investigator determines it is in the best interest of the patient. The reason for the treatment discontinuation should be recorded on the appropriate eCRF.

Treatment discontinued patients will not be replaced or allowed to re-start the study treatment. However, they should be strongly encouraged to stay in the study and undergo as many scheduled visits as possible with emphasis on the Weeks 48 and 96 visits.

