4.5 EFFICACY ANALYSIS

Efficacy analyses will be based on the ITT patient population or microperimetry-analysis population, as appropriate (Section 4.1.1), with patients grouped according to the treatment assigned at randomization. Available data from all randomized and treated patients regardless of adherence to the protocol will be included in the efficacy analyses; this includes data from patients who discontinued study drug early but continued with study assessments.

Unless otherwise noted, hypothesis testing and estimation of treatment effects will be performed with a regression model that includes data from all three treatment arms (sham pooled, lampalizumab Q4W, and lampalizumab Q6W). When analyzing data by biomarker group, separate regression models will be fit for the biomarker-positive and biomarker-negative patient groups (as defined in Section 2.2). All hypothesis tests for efficacy endpoints will be two-sided.

Unless otherwise noted, analyses of efficacy endpoints (primary, secondary, and exploratory) in the overall patient population will be adjusted for the following randomization stratification factors and baseline covariates:

- Biomarker status (positive vs. negative, as determined by the cobas[®] CFI Profile CTA)
- Baseline BCVA ETDRS chart Snellen equivalent (20/50 or better vs. worse than 20/50)
- Sex (male vs. female)
- Baseline GA lesion contiguity (multifocal vs. non-multifocal)

- For efficacy endpoints based on GA area and microperimetry assessments (e.g. number of absolute scotomatous points) only.
- Baseline GA lesion location (subfoveal vs. non-subfoveal)
 - For efficacy endpoints based on GA area, microperimetry assessments (e.g. number of absolute scotomatous points), and visual acuity (BCVA or LLVA) only.

Analyses of efficacy endpoints performed by biomarker group will include the above listed randomization stratification factors and baseline covariates with the exception of biomarker status.

All patients are expected to have the randomization stratification factors and baseline covariates that are specified above. One exception is that a small number of patients do not have a valid baseline BCVA score recorded per the corresponding electronic case report form. In order to include these patients in the efficacy analyses based on regression modeling with covariate adjustment, the BCVA category (20/50 or better vs. worse than 20/50) captured in the IxRS will be used.

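### Protocol 4.4.2 does not say whether needing a prohibited therapy ends study treatment only or study follow-up too, which can cost avoidable and possibly informative Week 48 and Week 96 data

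*Protocol*

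**What the plan says.** Protocol Section 4.4.2 describes the listed therapies as "prohibited from use during the patient's participation in the study treatment", and then says that "patients will be discontinued from study treatment and/or study to receive these therapies". Nothing there tells a site when to choose one exit, the other, or both. One item reaches the fellow eye: "Intravitreal anti-VEGF agents (other than Lucentis) in either eye". Two items, ocular corticosteroids by certain routes and Visudyne, concern the study eye. The rest are systemic or general.

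Elsewhere the plan wants follow-up kept. Section 3.1 says that patients stopped early from study treatment "will be encouraged to undergo as many scheduled visits as possible with emphasis on completing Week 48 and Week 96 visits". Section 4.6.2 says of the same patients that "they should be strongly encouraged to stay in the study and undergo as many scheduled visits as possible". SAP Section 4.5 uses all available data regardless of protocol adherence, and adds that "this includes data from patients who discontinued study drug early but continued with study assessments".

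Two other passages bear on the point. Section 4.4.1 lets a patient on study treatment receive Lucentis "if they are diagnosed in either eye with an ocular condition for which Lucentis is approved in the country". Section 4.6.1 gives the investigator a general right to withdraw a patient from the study at any time. Sections 4.6 and 4.6.1 also say that patients who leave the study are not replaced, and Section 4.6 does not let them re-enter.

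**The concern.** Two sites can both comply with Section 4.4.2 and produce opposite data: one keeps imaging the patient to Week 96, the other closes the patient's follow-up. The second loses intention-to-treat data that the SAP would have used, without any withdrawal of consent.

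The loss need not be random. Some triggers (study-eye corticosteroids, Visudyne, anti-VEGF) can follow events in the study eye or complications of injection. Protocol Section 5.1 lists ocular inflammation among the issues possibly tied to the route or pharmacology of lampalizumab, and under Appendix 6 sham patients receive no intravitreal injection. A difference between arms is therefore plausible, while the primary repeated-measures model assumes missing at random (SAP Section 4.5). When the trigger is anti-VEGF in the fellow eye alone, the study-eye autofluorescence image is not made invalid by that treatment, yet it may never be taken.

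**Working it through.** **The passages side by side**

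1. *What the ban requires.* It runs only while the patient is on study treatment. Stopping study treatment already satisfies it, so leaving the study serves no purpose that Section 4.4.2 states.
2. *How graver events are handled.* Table 4 in Section 4.4.3 deals with intraocular inflammation of 3+ or more, study-eye endophthalmitis and rhegmatogenous retinal detachment by ending study treatment only. If the same inflammation were treated with an intravitreal, subtenon or chronic topical steroid, Section 4.4.2 would also allow exit from the study. One patient can fall under both rules.
3. *What the analysis can use.* SAP Section 4.5 keeps data collected after study drug stops. The analysis gains nothing from ending follow-up.
4. *What covers the missing data.* For GA area, SAP Section 4.5.1.4 plans a sham-based pattern-mixture analysis and a tipping-point analysis, both missing-not-at-random. The early termination visit includes autofluorescence imaging (Appendix 1), and SAP Section 2.5 admits such images up to Study Day 384. For the three key secondary endpoints, Protocol Section 6.4 promises sensitivity analyses with details in the SAP, but SAP Sections 4.5.2 and 4.5.2.1 name no missing-not-at-random analysis. An early termination measurement is also not necessarily a Week 96 one.

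**The planning figure**

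Inputs from SAP Section 2.3.2: 312 per lampalizumab arm, pooled sham 2 × 156 = 312, SD 1.53 mm², target 0.42 mm², two-sided alpha 0.0496, dropout 15%.

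- Completers per arm: 312 × 0.85 = 265.2.
- SE = 1.53 × √(2/265.2) = 0.133 mm².
- Power = 88.5% (normal) or 88.3% (noncentral t). The SAP states 88%, so it reproduces.

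**Loss of numbers alone**

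Power by total dropout (noncentral t): 15% gives 88.3%, 17% gives 87.6%, 20% gives 86.4%. A few extra exits cost little power. The possible harm is bias.

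**Illustrative bias**

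Neither the rate of such exits nor their unseen outcomes are in the documents, so both inputs are assumptions. Let f be the difference between arms in the share removed, and D the amount by which the removed patients' unseen Week 48 mean departs from the missing-at-random prediction. Bias = f × D. Take f = 2 points, which is 0.02 × 312 ≈ 6 patients.

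| D (mm²) | Bias (mm²) | Share of 0.42 |
|---|---|---|
| 0.42 (equal to the target effect) | 0.02 × 0.42 = 0.0084 | 2% |
| 1.0 | 0.02 × 1.0 = 0.020 | 5% |
| 2.0 | 0.02 × 2.0 = 0.040 | 10% |

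At 0.0084 mm² the two-sided error stays at about 0.050 if the bias favours the drug, and power is about 87% if it works against it. At 0.040 mm² (0.040/0.133 = 0.30 SE) the corresponding figures are 0.060 and 82%.

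A wider grid, f from 1 to 5 points and D from 0.42 to 1.53 mm², gives 0.01 × 0.42 = 0.004 up to 0.05 × 1.53 = 0.077 mm², or 1 to 18% of the target.

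**The case against.** A reader might infer that Section 4.4.2 contradicts the retention rule. It does not. It permits study exit without requiring it, and once treatment stops the patient is outside the ban and within Sections 3.1 and 4.6.2, so a site can follow all three. What stands is that another site can end follow-up and also comply.

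A reader might also infer that the rule creates outcome-related missing data. The documents show only that it could. Permitted Lucentis narrows the anti-VEGF trigger in both eyes, though only for patients receiving study treatment and for conditions approved in that country. Short-term topical steroids are not a listed trigger. Systemic immunomodulators and experimental therapies need not relate to GA progression.

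For Week 48 GA area the plan has real protection: earlier images enter the model, an early termination image is requested, SAP Section 4.3 summarises reasons for discontinuation, and two missing-not-at-random analyses are specified. These limit the damage, but they model lost values and do not recover them.

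Finally, Section 4.6.1 lets an investigator withdraw a patient in any case, so editing Section 4.4.2 cannot close every route. That is true. But its listed examples are consent, safety and the patient's best interest. Section 4.4.2 is the passage that names needing a listed therapy as a ground for leaving the study, and it words this as something that will happen.

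**Conclusion.** The point holds as an unreconciled ambiguity with an avoidable cost in data. Its size is unknown. Under the assumed 2-point imbalance and a departure of 0.42 to 2 mm², the bias is about 0.008 to 0.04 mm², or 2 to 10% of the 0.42 mm² target.

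It would be tempting to report an error rate of 0.060 or power of 82%. Those figures compute correctly but need the top of the assumed range: 2 mm² is 96% of the 2.08 mm² mean progression assumed in SAP Section 2.3.2. Nor do the documents show that every patient needing a listed therapy would be removed, or that such exits fall outside the 15% dropout already planned for.

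The concern is weaker for Week 48 GA area and stronger for the Week 96 key secondary endpoints, where follow-up is longest and no missing-not-at-random analysis is named. This is a cheap improvement to the plan and does not undermine the primary analysis.

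**What to change.** Reconcile Protocol Section 4.4.2 with Sections 3.1, 4.6.1 and 4.6.2 so that needing a listed therapy does not by itself end study follow-up. In practice, remove the study-exit alternative from the sentence and refer to the retention rule in Section 4.6.2, except where consent is withdrawn or safety grounds under Section 4.6.1 apply. Leave the therapy list and the treatment-stopping rule unchanged; the edit concerns data collection only.

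In the SAP Section 4.3 disposition summaries, tabulate study exits for this reason separately by arm, so that their effect on Week 48 and Week 96 missingness can be judged.

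The cost is one amended sentence, one extra row in a table, and some visits for patients off treatment, which Section 4.6.2 already asks for. The SAP cites a March 2017 data review and a May 2017 external interim analysis, so a change made at that stage would mainly protect Week 96 data.

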4.4.3 Dose-Interruption and/or Treatment Discontinuation Criteria

Study treatment interruption and patient discontinuation from the study treatment for adverse events will be determined using the criteria listed in [Table 4](#). If any of these criteria are met, treatment will be interrupted (or discontinued if applicable) and will not be resumed earlier than the next scheduled study visit. The reason for study treatment interruption/discontinuation should be recorded on the *appropriate* eCRF and, if applicable, on the Adverse Event eCRF.

Table 4 Dose-Interruption and Treatment Discontinuation Criteria

Event	Dose-Interruption Criteria
Intraocular inflammation	Interrupt study treatment if intraocular inflammation (iritis, iridocyclitis or vitritis) is $\geq 1+$ in the study eye (see the grading scales of intraocular inflammation in Section 5.3.5 and Appendix 3). Patients with $\geq 3+$ intraocular inflammation will be discontinued from the study treatment.
VA loss	Interrupt study treatment if there is a treatment-related decrease in BCVA of ≥ 30 letters in the study eye compared with the last assessment of BCVA prior to the most recent treatment. Study treatment may be permitted subsequently as determined by the Sponsor and investigator.
Elevated IOP	Interrupt study treatment if IOP in the study eye is ≥ 30 mm Hg. Treatment may be permitted when IOP has been lowered to < 30 mm Hg, either spontaneously or by treatment, as determined by the investigator.
Vitreous hemorrhage	Interrupt study treatment in the event of a vitreous hemorrhage in the study eye. Study treatment may be permitted subsequently as determined by the Sponsor and investigator.
Rhegmatogenous retinal break	Interrupt study treatment if a retinal break is present in the study eye. Study treatment may be resumed no earlier than 30 days after successful laser retinopexy as determined by the investigator.
Rhegmatogenous retinal detachment or macular hole	Discontinue patients from study treatment for the duration of the study if rhegmatogenous retinal detachment or Stage 3 or 4 macular holes is observed.
Active local or systemic infection	Interrupt study treatment if any of the following are present: infectious conjunctivitis, infectious keratitis, infectious scleritis, or endophthalmitis in either eye or if the patient is currently receiving treatment for an active local or systemic infection. Patients with endophthalmitis in the study eye will be discontinued from the study treatment.

BCVA=best corrected visual acuity; IOP=intraocular pressure; IV=intravenous; VA=visual acuity; YAG=yttrium aluminum garnet.

Table 4 Dose-Interruption and Treatment Discontinuation Criteria (cont.)

Event	Dose-Interruption Criteria
Cataract surgery in study eye	Interrupt study treatment after cataract surgery in study eye. Study treatment may be resumed no earlier than 30 days after an uncomplicated cataract surgery and no evidence of post-operational inflammation. For cataract surgery with complications, study treatment may be permitted as determined by Sponsor and investigator.
Oral corticosteroids (prednisone >10 mg/day or equivalent)	Interrupt study treatment. Study treatment may be resumed when oral corticosteroids dosing is prednisone ≤10 mg/day or equivalent.
IV corticosteroids	Interrupt study treatment. Study treatment may be resumed when the patient has finished IV corticosteroid course and oral corticosteroid dosing is prednisone ≤10 mg/day or equivalent.

BCVA=best corrected visual acuity; IOP=intraocular pressure; IV=intravenous; VA=visual acuity; YAG=yttrium aluminum garnet.

If a patient misses more than 2 doses of study treatment within any 24-week treatment period, the investigator and the Sponsor may consider discontinuing the patient from the study treatment.

